## Background

Asthma disproportionately affects low-income and minority children residing in inner cities such as the Bronx, NY. Use of national guidelines reduces asthma morbidity by 70%; yet, these guidelines are not consistently implemented. For example, providers' failure to document symptom severity and control in the medical record can lead to inadequate prescription of controller medications. Providers also often fail to assess patients' inhaler technique, identify in-home exposures, and evaluate asthma co-morbidities. Asthma education and action plans are not consistently provided. System-level barriers found in our research include limited access to resources (e.g. sample MDI-spacers) necessary to follow the recommended care. Provider-level barriers include lack of awareness, disagreement with the guideline recommendations, lack of self-efficacy for being able to carry out the best practice, low expectation that outcomes will improve, and external barriers such as time constraints during a visit. Patient factors may affect adherence to preventive medications. Many parents have uncertainty about the effectiveness of medications, lack understanding about proper use of preventive medicines and administration devices, and have concerns about potential side effects. Other factors, such as financial barriers and problems with access to care have also been reported. There are missed opportunities to improve asthma care within the context of the child's medical home, particularly during clinic visits that are not asthma-related. A recent AHRQ review of interventions to improve provider adherence to national asthma guidelines concluded that systems-level interventions that address barriers and all the elements of the asthma care process (i.e., prescription of controller medication, environmental control practices, self-management education, documentation of severity and control) are needed. Although interventions to improve provider adherence to asthma guidelines have been described, few studies address translation of guidelines into routine care.

The proposed translational study builds on our experience evaluating a Multifaceted Prompting Intervention (MPI) in 12 urban clinics. MPI uses guideline-based prompts at the time of an office visit to support providers' decision-making, increasing the likelihood that they will recommend corrective actions (i.e., preventive medication prescription) to improve asthma management. We found that MPI delivered at one visit led to improved preventive care and short-term clinical outcomes (defined as number of symptom-free days (SFDs)). Although effective, this intervention must be modified in several ways to translate into practice.

Our earlier study found that one-time prompting did not improve long-term clinical outcomes, so support at multiple visits is warranted. Further, MPI was implemented by the research team to a sample of children with persistent asthma. Successful translation means that guideline-based care is delivered by providers and staff to all children with asthma, rather than just a research sample. The prompt was printed on paper, rather than delivered through the electronic health records (EHR), limiting wide-scale adoption. Further, the original study did not offer support for caregivers to follow through on providers' recommendations (e.g., filling prescriptions, ongoing self-management, medication adherence). Although providers are directly responsible for making healthcare recommendations to patients, delivery of guideline-based care requires all clinic staff to facilitate

communication, make changes to clinic work flow, and ensure patients and caregivers are able to follow recommended corrective actions. In order to translate MPI to pediatric practices, we will enhance it in several ways: (1) use clinic rather than research staff to facilitate assessment for prompts at every visit; (2) ensure prompting for guideline-based care for all children ages 2-12 with persistent or uncontrolled asthma, rather than just a research sample; (3) routinely deliver prompts to the provider via EHR; (4) offer telephone-based care coordination, education and support to children with the highest morbidity via a dedicated Outreach Worker (OW) to ensure recommendations are followed; and (5) provide practice-level supports (e.g. clinic champions, on-going performance feedback and participatory problem solving) to promote full adoption of guidelines. The enhanced MPI program (**eMPI**) consists of innovative multi-level and team-based strategies to enable providers to effectively and efficiently adopt asthma care guidelines.

We will conduct a cluster randomized trial comparing eMPI to enhanced usual care (eUC) in 22 Bronx practices serving over 5,000 children ages 2-12 years with persistent or uncontrolled asthma. Eleven eUC practices will receive guideline information and assess children's asthma severity and control, but active intervention components will not be provided. Practices will join the study in 4 waves over 4 years (4-6 practices per year). Including attendings and residents we anticipate enrolling an estimated 200 providers into the study.

## Study Objectives

This study has the following objectives:

**1. To test the impact of eMPI on provider adoption of asthma management guidelines.** The primary outcome is a clinic-level variable measured by the proportion of visits with  $\geq 1$  guideline-based corrective actions, as indicated in the EHR (i.e., controller medication prescription or adjustment, trigger evaluation). In this analysis we will include all patients ages 2-12 years with persistent or uncontrolled asthma (~5,000).

**Hypothesis 1 (primary):** eMPI will improve provider adoption of asthma guidelines compared to eUC.

**2. To determine whether consistent use of eMPI leads to both short- and long-term improvements in clinical outcomes.** Our main clinical outcome is improvement in SFDs. Since these data are not in the EHR, we will randomly sample 512 children's caregivers from eMPI and eUC practices. Caregivers will be interviewed every 3 months to examine short- (at 3 months) and long-term (at 6-12 months) change in SFDs.

**Hypothesis 2a (secondary):** Short- and long-term improvements in SFDs will be greater in eMPI over eUC.

**Hypothesis 2b (secondary):** We also will assess if these improvements are mediated by corrective actions taken at the visit.

**3. To evaluate the process of program implementation.** We will apply the RE-AIM framework to address the intervention's Reach (the provider-level proportion of visits with corrective actions), Effectiveness (provider corrective actions and SFDs), Adoption (the pace and level of uptake of guidelines), Implementation (improvements in reach and effectiveness over successive waves), and Maintenance (sustainable use of guidelines). We will evaluate group differences in the extent of healthcare utilization and resources used (i.e., adherence to clinic follow-up visits, specialty referrals, emergency and in-patient care, OW referrals).

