medication use, exposure to triggers, and specific tailored recommendations for guideline-based preventive care (e.g. for persistent asthma without controller medication, the recommendation on the prompt will include starting controller medication). For children with poor control despite being on controller medications, recommendation will include evaluation of inhaler technique and medication adherence, treatment and referral for evaluation of co-morbidities (e.g., referral to the Asthma Center for allergy and pulmonology consultations), "step-up" of medications, evaluation and counseling on triggers, and outreach worker referral (See below). The prompt will also include a recommendation for the provider to establish treatment goals with the patient and inquire about any caregiver's concerns. The prompt for the provider will be seen on the computer screen in EPIC EHR at the time of the visit allowing provider to check off the guideline-based recommended items discussed during the visit. The *caregiver prompt* will include immediate feedback on child's asthma severity/control with personally tailored information highlighting caregiver's goals and concerns. The prompt will include simplified recommendations for preventive care issues to discuss with the provider during the visit (e.g., to discuss triggers, medication concerns, need for asthma action plan (AAP) and medication administration form (MAF) for school). AAP and MAF are embedded into EPIC EHR patient chart and can be printed and given to patient to take home or to school. The caregiver prompt is based on the guideline recommendation to promote joint discussions about treatment plan and goals and will be printed for caregiver to bring to the visit. *Outreach worker* (OW)-delivered telephone-based care coordination and support will be provided by the bilingual (English/Spanish) OWs, lay people from the community who have asthma or a child with well-controlled asthma. OWs will become a practice-based resource. OWs will provide telephone-based care coordination, education and support to children who are already on controller medication but still have uncontrolled asthma and other barriers to guideline-based care (e.g., unable to fill a prescription, loss of medical insurance, poor medication adherence, gaps in caregiver knowledge despite provider education). The decision to refer family to OW service will be based on provider's assessment at any office visit. Providers will be prompted to make OW referrals for children with uncontrolled asthma as part of the guideline-based care. We estimate that 20% of children in each intervention practice will be referred to the OW. Providers will have a referral mechanism embedded within EHR to refer patients to the OW with suggestions on which children should be referred. *OW training:* OWs will be trained (4-weeks) by the PI ([name]) and Co-Is ([name], [name]) using evidence-based guidelines on asthma self-management skills, proper inhaler technique, triggers, medication use, goal setting and problem solving. The PI will oversee OWs with bi-weekly (and more often if needed) meetings to discuss cases/concerns and will listen to 20% of the recorded telephone calls to ensure the OWs deliver the sessions as intended. *OWs role:* OWs will help facilitate implementation of the guideline-based care prescribed by provider at the office visit. If referred to the OW at the initial visit, the first OW telephone call with the child's caregiver will occur within 2 weeks after the initial visit to determine any care coordination needs (e.g., assistance scheduling specialty appointments, inability to fill prescriptions) and then monthly, starting at 1-month post-initial visit for 6 months. If referred at the follow-up office visit, the same

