
implementation period as they conduct the severity/control asthma screening, make note of their screening practices and provide feedback to the nursing staff and the clinic champion. During the consolidation phase, we will continue to work with site champions and practices to ensure eMPI is implemented as intended and provide support on addressing barriers or concerns. Major activities during this time will include on-going monitoring of all aspects of eMPI, feedback to sites about their performance, identification of barriers and needed resources, and Board meetings to address these impediments. Given the COVID-19 pandemic, as of March 2020, Board meetings have been restricted to telephonic or video conference call only. We will finalize a sustainability plan with each practice to ensure on-going use of guidelines. During sustainability phase, we will observe practices' continued use of guideline-based care. During this time, we will not provide regular consultations or support, but will be available to address questions and concerns that arise. This will allow us to monitor how much outside help sites require to sustain eMPI. We will provide feedback at the practices' request. We expect that eMPI practices undergoing our translational program will increase guideline-based care during a 3-month initiation period and subsequent 3-month consolidation period, and will maintain these gains over an 18-month sustainability period.

**Enhanced Usual Care (eUC) Practices** will receive a review packet of the NAEPP guidelines and educational resources for families. Children will be assessed for asthma severity and level of control at each visit as best-practice care, but active intervention components will not be provided.

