#### **Clinic-Level Variables**

The **primary outcome** is a clinic-level variable measured by the proportion of visits with  $\geq 1$  guideline-based corrective actions. To calculate this proportion, the denominator will include only the visits by patients aged 2-12 years with persistent or uncontrolled asthma at the time of visit. We will obtain these data from the EHR at baseline, monthly during the initiation phase (to provide feedback to eMPI practices) and every 3 months thereafter for 24 months. Corrective actions include: (1) prescription of a new preventive asthma medication; (2) increase in dose of a preventive medication (for children already on preventive medication); (3) evaluation and counseling regarding triggers; (4) treatment of co-morbid conditions (e.g., sinusitis, allergic rhinitis, obesity); (5) referral to an allergy or pulmonary specialist. We will consider children receiving any of these guideline-based preventive care measures during the visit as having a corrective action (as not all actions may be necessary for each patient), and also will consider each component of preventive care separately. We collected prospective data on most items included in the corrective action definition in our prior work. Additional corrective actions include recommendations for a follow-up visit specifically to discuss asthma, referrals made to OW, and provision of an asthma action plan or school medication administration form.

**Covariate:** Practice characteristics will include practice size (small, medium, large), practice type (hospital-based practice, Federally Qualified Health Center, neighborhood health center), and patient mix (pediatrics, adult/pediatrics), involvement of support staff in the delivery of preventive asthma care, practice-level changes (e.g., new asthma-related initiatives in the practice). We will obtain this information from the existing database of practices and from interviews with the physician champion and office administrator at each practice.

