#### **Data and Safety Monitoring Plan**

##### Data Quality Monitoring

Baseline data forms will be completed electronically by research staff on Tablet PCs in the waiting room. All survey data collected on the Tablet PCs are entered using data entry forms created by Adobe Creative Suite 3 software, which allows for integration with secure data entry forms to an off-site server. Asthma severity and control assessment and data necessary for generation of the prompts will be entered into each patient's EPIC Electronic Health Record (EHR). For the safety of private subject information, no data will be stored on the Tablet PCs. For the 4 follow-up telephone interviews, data will be collected using RedCap database. Pre-intervention training of study staff will be conducted to increase knowledge about asthma, asthma medications, and other important information in order to reduce the number of "real-time" data collection errors. Through this training, staff will note any inconsistencies in parent reported data and will discuss them with the parent at the time of the interview.

A separate team of researchers will perform all follow-up interviews and follow-up data management. This group will work independently from the "enrollment team" and thus will be able to perform blinded assessments of outcomes. Randomization information will not be included with any follow-up materials in order to assure blinding of outcome assessment.

Once data have been collected, simple range checks as well as cross-form validation checks will be performed to ensure the accuracy and completeness of the data. A list of all data checks performed will be maintained and any errors detected by this method will be noted. In addition, data forms, valid informed consent documents for each enrolled patient, and supporting source documentation materials will be reviewed by the data analysts for accuracy. Required regulatory documents (IRB approval, updates to the protocol, data monitoring documents) will be maintained by the study coordinator. All events during the course of the trial including study enrollments, adverse events and study terminations will be reported to the study coordinator (see safety section below).

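### The primary outcome has two component lists that do not match, and the plan does not say whether outreach worker referral and other further actions count

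*Combined protocol and SAP*

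**What the plan says.** Three places describe what makes a visit a success for the primary outcome.

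- **Study Objectives, objective 1.** The outcome is the proportion of visits with at least one corrective action, "as indicated in the EHR (i.e., controller medication prescription or adjustment, trigger evaluation". Introduced by i.e., this reads as a complete list of two items.
- **Measures, Clinic-Level Variables.** Under the primary outcome label there are five numbered items. The medication items are "1) prescription of a new preventive asthma medication" and "2) increase in dose of a preventive medication (for children already on preventive medication". The others are "3) evaluation and counseling regarding triggers; (4) treatment of co-morbid conditions (e.g., sinusitis, allergic rhinitis, obesity); (5) referral to an allergy or pulmonary specialist". Receiving any one makes the visit a success, and each component will also be looked at separately. The same paragraph ends by naming further corrective actions: advising an asthma-specific follow-up visit, referring to the OW, and giving an asthma action plan or school medication form. It does not say whether these enter the primary outcome.
- **Summary of Analytic Plan, Aim 1.** The outcome ratio again uses at least one action. The null hypothesis instead speaks of the actions that were necessary. No components are listed and neither earlier section is cited.

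**The concern.** This is the trial's single primary endpoint, extracted from the health record and scored by an any-one rule. Under such a rule, adding or removing one item reclassifies every visit where that item was the only action. The short list is not just an abbreviation of the long one. It omits two items that the long list credits, and its broader terms (adjustment, evaluation) admit events that the long list leaves out.

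The status of the further actions matters more. OW support is listed among the core elements of eMPI, while eUC practices receive no active intervention components. If an OW referral alone makes a visit a success, eMPI practices have a route to success that eUC practices lack, whatever happens to controller, trigger, co-morbidity or referral care. As long as the list is open, the choice could also be made after results are known.

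**Working it through.** **1. The plan's power figure.** Inputs from the Aim 1 Power Analysis: mean paired difference 0.25, SD of paired differences 0.20, 11 pairs, two-sided 0.05, paired t approximation with 10 df.

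Noncentrality = (0.25 / 0.20) × √11 = 1.25 × 3.317 = 4.146. The noncentral t distribution with 10 df gives power of 96.1%, which agrees with the stated figure of more than 95%. No component rate enters this calculation. The SD comes from mock data sets and the 25 points from the investigators' estimate; neither is tied to a list. With the same two inputs, either list gives the same 96.1%.

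**2. Scoring the same visit under each text.** Each row is a visit where the named event is the only action (1 = success).

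| Only action at the visit | Objective 1 | Five numbered items | Five items plus further actions |
|---|---|---|---|
| Allergy or pulmonary referral | 0 | 1 | 1 |
| Co-morbidity treatment | 0 | 1 | 1 |
| Controller adjusted, no new drug or dose increase | 1 | 0 | 0 |
| Trigger evaluation without counseling | 1 | 0, if item 3 needs both | 0, if item 3 needs both |
| OW referral | 0 | 0 | 1 |
| Action plan or school form | 0 | 0 | 1 |
| Asthma follow-up visit advised | 0 | 0 | 1 |

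Four rows differ between the first two columns, two in each direction. The last three rows depend on an unstated rule.

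**3. Can the direction of the effect be derived?** No; the documents give no visit rate for any component. The following rates are assumptions, used only to show that the sign is open. Suppose the two-item list gives 40% (eUC) and 65% (eMPI), a difference of 25 points, and an added action occurs independently at rate q. The new proportion is 1 − (1 − p)(1 − q).

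- Added action at 20% in both arms: 1 − 0.60 × 0.80 = 0.52 and 1 − 0.35 × 0.80 = 0.72. The difference is 20 points, so it shrinks.
- Added action at 10% in eUC and 30% in eMPI: 1 − 0.60 × 0.90 = 0.46 and 1 − 0.35 × 0.70 = 0.755. The difference is 29.5 points, so it grows.

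The second case is not far-fetched: the eMPI prompt itself recommends co-morbidity treatment and specialist referral for poorly controlled children already on controllers.

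**4. OW referral.** If OW referral counts, the eMPI proportion rises by the share of visits where it is the only action, and no matching term exists in eUC. The plan expects 20% of children in each intervention practice to be referred. That figure is per child, not per visit, and the overlap with other actions is not given. The rise therefore cannot be computed; only its direction is known.

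**The case against.** The strongest reply is that the Clinic-Level Variables section is already the working definition. It has the denominator, extraction schedule, numbered items and any-one rule, whereas objective 1 has only a parenthesis. The authors also use i.e. loosely elsewhere: the Background glosses corrective actions as preventive medication prescription alone. This is fair and settles which text should govern. It does not remove the conflict, because no text says that it governs, and the ambiguity over further actions lies inside that same section.

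The medication difference may also be small in practice, since a switch of controller could be recorded as a new medication and the adjustment that the prompt describes for poor control is a step-up. That may be so; the documents give no count of such visits.

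Two stronger readings are tempting and are not supported.

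- **That the mismatch costs power.** A reader might compute losses from assumed component rates. The list is not an input to the stated power, every such rate would be invented, and step 3 shows that the difference can also grow.
- **That triage data create a false eMPI effect.** The eMPI prompt shows "medication use, exposure to triggers, and specific tailored recommendations for guideline-based preventive care", and "data necessary for generation of the prompts will be entered into each patient's EPIC Electronic Health Record (EHR". For eUC the plan says "Children will be assessed for asthma severity and level of control at each visit as best-practice care". A reader might infer that triage trigger answers would count as evaluation in eMPI only. But the Screening paragraph places a triage survey in the health record at all practices, citing the same Appendix A as the eMPI text. That appendix is not available here, so an arm asymmetry is not established. The eMPI text also separates displayed trigger exposure from the recommended provider action of evaluating and counseling. What stands is narrower: no text excludes a triage answer from the trigger item, so one sentence should do so.

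**Conclusion.** Wrong as written. The two descriptions of the primary outcome do not match, the analysis section points to neither, and the status of the further corrective actions is left open. Some visits score differently, in either direction, so the estimated effect can change. Its size and direction cannot be derived from the documents, and the stated power is unaffected. Counting OW referral is the one case where the direction is known: it can only add to the eMPI proportion. This rests on reading OW support as exclusive to eMPI, as the intervention and eUC descriptions indicate. The scoring of trigger evaluation without counseling rests on reading item 3 as requiring both.

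**What to change.** 1. Make the numbered five-item list under Clinic-Level Variables the sole definition of a corrective action for the primary outcome.
2. Replace the parenthesis in objective 1 with a reference to that list. In Aim 1, replace the wording about necessary actions with at least one action from the same list.
3. State that the further actions, OW referral in particular, do not count toward the primary outcome and are reported separately. Aim 3 already examines OW referrals as utilization.
4. State that the trigger item requires provider counseling recorded at that visit, and that a triage survey answer does not meet it.

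A narrower composite (medication and trigger items only) is optional, since the plan already intends to look at each component separately.

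The cost is protocol and SAP wording plus explicit extraction rules; no new data collection is needed. The downside is that the observed effect may be smaller than under a looser definition.
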